7.3 RANDOMIZATION

Women who have met all inclusion criteria and have none of the exclusion criteria, and who have signed the informed consent, will be scheduled for a randomization visit. Prior to the randomization visit all women who did not have a blood collection at the screening visit will be advised to fast for at least twelve hours prior to the visit. A blood sample will be collected for central analysis and a local sample for assessment of INR if needed. Data to be collected are indicated in Table 2.

Randomization to one of the four possible study groups (active HRT and placebo antioxidants, active HRT and active antioxidants, placebo HRT and active antioxidants, placebo HRT and placebo antioxidants) will be by a telephone call to the Study Coordinating Center. After confirmation of the patient's eligibility the SCC will issue a

unique patient identifier and medication codes that the clinical center coordinator will use to obtain the woman's study medications. The unique patient identifier will be used on all study forms, laboratory samples, angiograms and any other necessary study documents. Each woman will have a one in four chance of being assigned to each of the four study groups. Randomization will be stratified by clinical center (n=5) and by whether a hysterectomy has been performed. Each woman will be given a seven month supply of her study medications, a medication instruction sheet, a bleeding calendar for those women with a uterus, a bottle of Centrum Silver vitamins (if she requests it), and an appointment for the one month visit.

TABLE 2

WAVE Summary	Screening	Randomization	IM	3M	6M	12M	18M	24M	30M	36M	Exit
Consent	X										
Creat, trig, FSH (if needed)	X										
INR	Obtain at either visit		X								
Study Bloods	Obtain at either visit			X			X			X	
Ht/wt, BP, waist/hip	Obtain at either visit					X		X		X	
Randomization form		X									
Breast, pelvic, Pap, mamm, breast self-exam teaching	X					X		X		X	
Sign medical release	X					X		X		X	
Brachial reactivity	Obtain between consent and initiation of study medication			X							
Dipyridamole SPECT/ETT				X						X	
ECG		X				X				X	
Patient tracking form		X			Update as needed						
Bleeding calendar		X	X	X	X	prn	prn				
Dispense study meds		X			X	X	X	X	X		
Adherence assessment					X	X	X	X	X	X	X
Quality of Life		X		X			X		X		
Follow-up visit*					X	X	X	X	X	X	X
Angiogram	X										X
Physical exam		X				X		X		X	

*Includes: side effects, concurrent medications, internal medical history and adherence

7.4 SCHEDULED FOLLOW-UP

Following randomization all WAVE trial participants will be scheduled for visits at 1, 3, 6, 12, 18, 24, 30 and 36 months. In addition a woman who was randomized during the early months of recruitment, may require a 42 and possibly a 48 month visit. The actual number of visits will depend on the date of randomization and the occurrence of interim fatal or non-fatal events. The requirements of each visit are summarized in Table 2.

7.4.1 One Month Visit

The one month visit serves to reinforce the relationship between each randomized woman and the local WAVE clinical center staff, including her gynecological contact. Any initial side effects and management options will be discussed and agreed upon. No measure of adherence will be obtained at this visit. For women on Coumadin, an INR will be assessed locally and the three month follow-up visit will be scheduled.

7.4.2 Three Month Visit

The patient will be asked to fast for at least twelve hours before the visit and a study blood sample will be collected for central analysis. A designated individual will discuss any symptoms or side effects identified by the patient. For those women participating in either the brachial reactivity or SPECT/ETT study, the appropriate assessments will be performed and the six month visit scheduled. No measure of adherence will be collected.

7.4.3 Semi-Annual Visits (at 6, 18, 30 and, if necessary 42 months)

The participant will be asked to bring in all unused study medication and all other medications she has taken since the last study visit. For the 18 month visit, the participant will be asked to fast 12 hours before visit. During each semi-annual visit a designated individual will

review and discuss any symptoms potentially attributable to either study medication. The coordinator or his/her designee will:

1. Document any clinical outcomes that have occurred since the last visit and record current medications on a follow-up form;
2. Record study medication capsule/tablet count on a follow-up form; dispense a new supply of study medication and provide a new bleeding calendar, if appropriate;
3. At the 18 month visit only, draw serum for fasting total cholesterol, HDL cholesterol and triglycerides assays;
4. Schedule the next appointment and remind the participant to call with questions.

7.4.4 Annual Visits (at 12, 24, 36 months)

The participant will be asked to bring in all unused study medication and all other medications she has taken since the last study visit. At the 36 month visit, the participant will be asked to fast 12 hours before coming to the visit. During each annual visit, a designated individual will review and discuss any symptoms potentially attributable to either study medication. The coordinator or his/her designee will:

1. At the 36 month visit, draw fasting study bloods for processing and shipping to the central biochemistry laboratory. Feed participant if desired. At the 36 month visit (42 month for some women), obtain pre-angiogram bloods, if necessary;
2. Document any clinical outcomes that have occurred since the last visit and record current medications on a follow-up form;
3. Record study medication capsule/tablet count on follow-up form; dispense a new supply of study medication;

4. At the 12 and 36 month visits obtain an ECG;
5. Perform a breast examination, provide breast self-exam teaching, perform pelvic examination, obtain a Pap smear (if uterus present and none done within past 12 months) and complete the physical exam form;
6. Ask participant to sign a medical release. Make arrangements to obtain any mammogram report done within the past 12 months, or schedule a mammogram;
7. At the 36 month visit (42 month for some women), schedule the exit angiogram and the visit.
8. At the 36 month visit, perform appropriate assessments for patients in the Effects of Hormone Replacement Therapy on Electrocardiographic and Scintigraphic Measures of Myocardial Ischemia Study.

Comment [TBC2]:

7.4.5 Exit Visit

This visit will take place after the final angiogram of the patient. During the visit, the coordinator or his/her designee will:

1. Discuss results of angiogram.
2. Reinforce participant's valued contribution to the study. Discuss treatment options until the entire cohort is unmasked at the end of the trial.
3. Discuss the procedure for informing the participant and her designated physician of the trial's results.

7.4.6 Additional Visits

Additional visits will be scheduled as required by the patient's health. These visits are not considered study visits and this protocol does not mandate particular procedures or data collection for such visits.

8. MONITORING OF ADHERENCE AND SAFETY

8.1 MONITORING ADHERENCE

Starting at the 6 month visit, and at each subsequent study visit, a measure of adherence to the assigned treatment regimens will be collected. Women will be asked to return all unused study medications at each visit. The study coordinator will ask each woman if there have been any problems adhering to the medication schedule. The coordinator will count the number of returned capsules/tablets. This will be used to estimate adherence to the protocol. To discourage out-of-trial use of vitamins and improve protocol adherence, patients will be provided with a multivitamin (Centrum Silver), with a minimal antioxidant vitamin content (60 mg C, 45 IU E, 6000 IU VitA-carotene), supplied to the trial by BASF/Knoll.

In addition to the capsule/tablet counts, plasma collected at baseline and 36 month visits will be analyzed for vitamins C and E. This will allow an additional measure to correlate with the capsule/tablet count data.

8.2 MONITORING PATIENT SAFETY

The NHLBI will appoint an independent Data and Safety Monitoring Board (see Section 12.2.1) to monitor all aspects of the WAVE trial. The SCC will prepare reports summarizing all aspects of the WAVE trial, including: screening, randomization, baseline, follow-up, adherence, side effects, and outcomes. In addition, specific requests may be made for additional reports by the DSMB. The DSMB will convene approximately every six months, either by telephone conference call or in person.

8.3 MONITORING POTENTIAL ANTIOXIDANT THERAPY SIDE EFFECTS

At high doses, vitamin E may result in a bleeding diathesis through its interaction with vitamin K dependent clotting factors and its antiplatelet effects. To monitor the former, all women will have a prothrombin time (INR) assessment prior to randomization and at the one month visit. If the patient is on an anticoagulant, the INR results will be sent to her private physician so that the anticoagulant dose can be appropriately adjusted to maintain the desired INR range. If anticoagulant therapy is initiated after randomization, this procedure will also be followed.

There are no specific side effects of vitamin C requiring laboratory tests for monitoring.

Data will be collected to estimate and compare the frequency of: hemorrhagic stroke; episodes of major (requiring a transfusion) and minor bleeding of other sites; renal stones; episodes of nausea or gastrointestinal upset.

If a patient cannot tolerate full doses of the study antioxidant medications due to nausea or other gastrointestinal side effects, dosage will be transiently reduced to 50 percent of the planned daily dose. Once the side effects have resolved, an attempt should be made to resume full doses of the medications. If this is not tolerated, patients will be maintained at 50 percent of the planned daily dose for the remainder of the trial.

Vitamin E/placebo therapy will be stopped after the occurrence of a hemorrhagic stroke. In the case of a major bleed at another site vitamin E/placebo therapy may be stopped temporarily or permanently at the discretion of the local WAVE investigator. If other predisposing factors (e.g., peptic ulcer, adjustment of Coumadin dosing, etc.) develop, modification or temporary discontinuation of vitamin E/placebo should be considered.

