12.2.2 Data and Safety Monitoring Board

The Data and Safety Monitoring Board is appointed by the Director of the NHLBI. The members, who are not otherwise affiliated with the study, include experts in cardiology, angiography, gynecology, use of antioxidant therapy, biostatistics, bioethics and other relevant disciplines. The DSMB reviews the Protocol for the main study, any proposed modifications to the Protocol, and the protocols for all proposed ancillary studies.

The members of the DSMB will monitor the progress of recruitment, compliance, data quality, clinical endpoint data, adverse drug responses and side effects. Prior to the end of the trial, summary endpoint data presented by randomization group is confidential and shared only with the DSMB. The DSMB will review reports approximately twice a year, either in person or by conference call, and make its recommendations concerning the conduct of the WAVE trial directly to the Director of the NHLBI. The Principal Investigator and Co-Investigators of the Study Coordinating Center, the NHLBI Project Officer and other designated Institute staff and the chairman of the Steering Committee are ex-officio members of the DSMB.

During the active recruitment phase, the DSMB will monitor the progress of recruitment and the random allocation of participants to treatment and control groups and may recommend modifications in recruitment goals and procedures as needed. At any time, the DSMB may recommend discontinuation of the study or one of its treatment arms on any of the following grounds:

- A. An adverse effect attributable to either of the study treatments that is sufficient to override any potential benefit and preclude its further use in post-menopausal women;
- B. compelling evidence from this or another study of a significant beneficial effect of either of the study treatments, such that its continued denial to the control group is ethically untenable;
- C. a very low probability of successfully addressing the study hypotheses within a feasible time frame, because of inadequate recruitment, compliance, etc.

The Director, NHLBI will make the final decision on whether or not to continue the study.

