12.2.3 Steering Committee

The Steering Committee is the representative body of study participants. The voting members of the Steering Committee include the Principal Investigator of each of the five clinical centers, the NHLBI project officer, and the Principal Investigator of the Study Coordinating Center. The Steering Committee provides overall scientific direction for the study through consideration of recommendations from the subcommittees. The business of the Steering Committee will be conducted in accordance with customary parliamentary procedures. The Steering Committee will meet at least once each year to review the progress of the study and to monitor non-endpoint data. The Steering Committee will not have access to endpoint data and treatment group differences until the trial is completed. The Steering Committee will establish subcommittees to support its objectives. The subcommittees currently include: Publications, Interventions, Quality of Life, End Points, Recruitment and Adherence, Laboratory, Conflict of Interest. The members of the subcommittees are appointed from among the investigators at the clinical centers, SCC, and NHLBI. The chairman of each subcommittee will be either a Principal or Co-Investigator from one of the clinical centers or the SCC.

All subcommittees have specific responsibilities outlined below and may assume other responsibilities as requested by the Steering or Executive Committees.

- A. Publications Subcommittee: decides on the timing and content of publications and presentations. They will review all study manuscripts prior to submission. They will review all research requests for use of study patients or any study data. They will forward their recommendation for each proposal to the Steering Committee.

- B. Interventions Subcommittee: Selected the HRT and antioxidant vitamins, specified the dosage and the management of side effects.

- C. Quality of Life Subcommittee: Selected the Quality of Life instruments to be used in the Quality of Life component of the WAVE trial.

- D. End Points Subcommittee: Will develop definitions and algorithms for angiographic and clinical endpoints. Will implement a mechanism for the timely, masked classification of clinical events by study cardiologists. Members will include the principal investigator of the Central Angiography Laboratory, a cardiologist from the SCC and investigators from the Clinical Centers.

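### Protocol 8.3 makes transfusion the only criterion for a major non-stroke bleed, so a critical-site bleed that needs no blood is not graded major (minor point, cheap to improve)

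*Protocol*

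**What the plan says.** Section 8.3 of the protocol starts from a named harm: "At high doses, vitamin E may result in a bleeding diathesis". It then lists what will be compared. The list opens with "Data will be collected to estimate and compare the frequency of: hemorrhagic stroke" and continues with "episodes of major (requiring a transfusion) and minor bleeding of other sites". Non-stroke bleeding thus has two grades. The upper grade has one criterion, the need for transfusion, and the lower grade has none.

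The same section ties drug management to these categories. Vitamin E/placebo is stopped after a hemorrhagic stroke. For other bleeding the wording is permissive: "In the case of a major bleed at another site vitamin E/placebo therapy may be stopped temporarily or permanently", at the local investigator's discretion.

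Three other places bear on the point:

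- Section 7.4.1 shows that anticoagulated women can be in the trial: "For women on Coumadin, an INR will be assessed locally".
- Sections 8.2 and 12.2.2 give the DSMB oversight of "clinical endpoint data, adverse drug responses and side effects" and add that "specific requests may be made for additional reports by the DSMB".
- Section 12.2.3 says of the End Points Subcommittee: "Will develop definitions and algorithms for angiographic and clinical endpoints". It also asks that subcommittee to set up masked classification of clinical events by study cardiologists. Bleeding is not named there.

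**The concern.** Transfusion need measures the volume of blood lost. Some bleeds are grave because of where they occur: a small intraspinal or intraocular bleed can cost function or sight without any need for blood. Under the printed rule such an event is not major, and the only other grade is minor, where it would sit with trivial bleeding.

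Section 8.3 already treats one site as grave whatever the volume, because hemorrhagic stroke has its own line and its own stopping rule. It does not extend that reasoning to other critical sites. Bleeding is the harm the section itself names for vitamin E, and the major-bleed line is where a reader looks for serious non-stroke bleeding. What is at stake is the severity grade of a few events on that line and, slightly, the wording that governs stopping.

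**Working it through.** The protocol gives no figure for bleeding, so there is none to reproduce. The check is mainly a reading of the rule.

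**Applying the rule in 8.3**

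1. Is the event a hemorrhagic stroke? If so, it goes on the stroke line.
2. If not, does it require a transfusion? If so, it is major.
3. If not, it is not major. Minor is undefined, but it is the only grade left.

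| Bleed, no transfusion needed | Stroke line? | Major under 8.3? |
|---|---|---|
| Intraspinal | No | No |
| Intraocular | No | No |
| Subdural or other intracranial | Unclear, because hemorrhagic stroke is undefined | Not if it is off the stroke line |

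The first two rows follow from the text alone. The third depends on how hemorrhagic stroke is read.

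**Is there another definition?** Section 12.2.3 assigns definitions and masked classification to a subcommittee but prints no bleeding criterion. Sections 8.2 and 12.2.2 cover reporting to the DSMB. No section of the protocol other than 8.3 defines major bleeding.

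**Scale, as illustration only.** The bleeding rates and the share of critical-site bleeds below are assumptions; none comes from the documents. The target of 450 women (section 10.4), split by the vitamin factor and ignoring dropout, gives 450 / 2 = 225 per group.

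- Expected serious non-stroke bleeds: E = 225 × (p1 + p2), where p1 and p2 are the assumed proportions in the two groups.
- Expected number not graded major: m = E × share, with an assumed share of 5% to 15%.
- Chance of at least one such event (Poisson): 1 − exp(−m).

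| Assumed p1 v p2 | E | m at 5% | m at 15% | Chance of at least one |
|---|---|---|---|---|
| 1% v 2% | 225 × 0.03 = 6.75 | 0.34 | 1.01 | 0.29 to 0.64 |
| 2% v 3% | 225 × 0.05 = 11.25 | 0.56 | 1.69 | 0.43 to 0.82 |
| 3% v 8% (upper case) | 225 × 0.11 = 24.75 | 1.24 | 3.71 | 0.71 to 0.98 |

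If intracranial bleeds mostly go on the stroke line, the share falls and so do these counts. The table shows only that a handful of events at most would be in question under these assumptions. It is not an estimate.

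**The case against.** The strongest reply has four parts.

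**The criterion is a reasonable choice.** Transfusion is objective and can be applied alike at five centers, and the critical-site category is not taken from the protocol. This stands as far as it goes: 8.3 contains no contradiction, and the point is an improvement to a stated criterion. The fix keeps the transfusion count for that reason.

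**Classification is delegated.** Section 12.2.3 provides for definitions and for masked classification of clinical events, and operational detail may sit elsewhere. The subcommittee may indeed refine the grade. But 8.3 prints a criterion, and masked classifiers who apply it as printed would still not grade these bleeds as major.

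**The subdural example is uncertain.** With hemorrhagic stroke undefined, a subdural bleed may belong on the stroke line. This stands. A reader might infer that subdural bleeds certainly drop to minor, and the text does not support that. The intraspinal and intraocular cases do not depend on it.

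**Safeguards exist.** Women with a history of hemorrhagic stroke or bleeding diathesis are excluded (section 3.3). Section 8.3 sets INR checks and sends anticoagulated women's results to their physicians. The DSMB sees side effects and may ask for more. All of this is true and limits the consequence, but none of it changes the grade.

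**Conclusion.** The point holds as a minor one. As printed, 8.3 does not grade as major a critical-site bleed that needs no transfusion: intraspinal, intraocular, or intracranial and not counted as hemorrhagic stroke. This applies to the vitamin E comparison and to the discretionary stopping sentence. The conclusion rests on the wording of 8.3 and on the absence of any other definition in the protocol. The number of events affected cannot be estimated from the documents and is probably very small.

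A reader might infer more, but the documents do not support it:

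- **Lost events.** Minor bleeding is also collected and compared, so only the severity grade is lost.
- **Bias.** The same rule applies in both masked groups, so no direction follows.
- **Loss of planned power or harm to the primary analysis.** The protocol states no power for any bleeding comparison. The primary endpoint is change in minimum lesion diameter, and neither it nor its sample size uses bleeding.
- **Women kept on drug after a grave bleed.** The stopping sentence permits and does not restrict; nothing in it bars an investigator from stopping vitamin E/placebo after a bleed without transfusion.
- **Omission of fatal bleeds.** A fatal bleed may often have required a transfusion, so no gap is asserted there.

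**What to change.** In section 8.3, define major bleeding at sites other than hemorrhagic stroke as bleeding that meets any one of these criteria:

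- it is fatal;
- it is at a critical site (intraspinal, intraocular, or intracranial and not counted as hemorrhagic stroke);
- it requires a transfusion.

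Listing fatal bleeds is for clarity. Wording the intracranial item this way means every intracranial bleed is either on the stroke line or major, however hemorrhagic stroke is later defined.

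Report the transfusion-only count as a second line, so the present measure is kept. Use the same definition in the sentence on stopping vitamin E/placebo after a major bleed at another site, and leave the decision discretionary.

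The cost is one definition in 8.3 and a matching item on the event form. The downside is a few more events to classify and a slightly higher reported major-bleed rate.

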8.4 MONITORING POTENTIAL HORMONE REPLACEMENT THERAPY SIDE EFFECTS

8.4.1 Symptomatic Management

Women will be instructed on palliative management of symptoms such as breast tenderness or bloating. The management of these side effects includes dietary changes, use of a mild diuretic for fluid retention, vaginal lubricants and reassurance. If these symptoms continue and are not tolerated, the dose of study hormone drug will be reduced in frequency to 5 days per week or less and then slowly increased to attempt to achieve the protocol dosing regimen.

8.4.2 Vaginal Bleeding

If bleeding occurs during the first six months post randomization, the patient will be managed by the following algorithm: a) If no endometrial aspiration or biopsy has been performed within the last twelve months, endometrial aspiration will be recommended for any bleeding. If the patient refuses and bleeding has stopped, she will continue on study drug and will be reassessed at the 6 month visit. If she has had further bleeding, endometrial aspiration will again be recommended. If the patient still refuses, consider vaginal ultrasound to measure endometrial thickness. If this is ≥ 5 mm, the patient should proceed to endometrial aspiration and the study drug be discontinued if she refuses. If the endometrial thickness is < 5 mm, she may continue on study drug (consider getting the patient's signature on a form describing that ultrasound is less sensitive for determining endometrial pathology than aspiration); b) If endometrial aspiration has been performed within the past twelve months, and was benign, no further assessment is warranted for one year post aspiration. However, if bleeding is heavy (soaking 1 or more pads per 24 hours) during the first six months however, endometrial aspiration will be recommended even if performed within the past twelve months.

If endometrial biopsy has been performed, the following algorithm will be followed based on the results of the biopsy:

1. Normal atrophy, secretory or proliferative continue randomized therapy. If insufficient tissue is available, a second biopsy should be obtained and a vaginal ultrasound performed.
2. Simple or complex hyperplasia. Stop randomized hormone therapy, and treat with medroxyprogesterone 10-20 mg qd for 2-3 months followed by repeat biopsy. If the repeat biopsy is negative, study drug may be restarted and the patient should be scheduled for follow-up biopsy in one year. If the woman starts to bleed once the study drug is restarted, consider adding medroxyprogesterone 2.5 mg daily to the study drug for 3 to 4 months. The additional medroxyprogesterone should then be stopped and the presence of bleeding reassessed on study drug alone. If the biopsy shows hyperplasia, the study hormone replacement therapy should be permanently discontinued and the patient referred to a gynecologist for further management.
3. Atypia or cancer. Stop study hormone replacement therapy and refer the patient to her private gynecologist or internist.

